## 6.9 Telephone Safety Follow-up (Day 181 $\pm$ 14 days, and Day 366 $\pm$ 14 days)

All participants will be followed for a minimum of 12 months from the time of enrollment in the study. However, the study will be unblinded when the safety data up to day 50 and data for primary and secondary endpoints have been collected for all participants. Any participant who experiences complications due to vaccine or placebo administration will be followed until resolution of such complications or appropriate referral to the necessary medical care has been made.

Follow-up visits will take place over a telephone call on days 181 and 366 (+/- 14 days). The study doctor will discuss ongoing, unresolved AEs with the participant and if deemed necessary, schedule a clinic visit. The procedures/evaluations to be conducted at these visits are shown in [Appendix A](#). The follow-up call on day 366 will be the final study intervention unless the participant requires additional follow-up of study-related complications.

## 7 Study Procedures/ Evaluations

### 7.1 Clinical and Laboratory Evaluations

See [Appendix A](#) for clinical and laboratory procedures performed during the vaccination and mosquito feeding visits as well as follow-up portions of the study. See [Appendix B](#) for Blood Volumes for Specimen Collection. Many of these tests are being performed to monitor safety and ensure that participants are healthy enough to undergo vaccination and mosquito feeding. The CVD has established limits for blood draws for research purposes, and the planned blood draws are within these limits.

#### 7.1.1 Laboratory Testing of Collected Samples for Primary and Secondary Endpoints

- AGS-v PLUS specific IgG, IgM and IgE assay will be performed using enzyme-linked immunosorbent assay (ELISA). The time points assayed will be day 1, day 43 and day 50.
- Th1 and Th2 response assays: PBMCs collected from participants will be incubated with AGS-v PLUS and saliva from *Aedes aegypti*, *Aedes albopictus* and *Anopheles gambiae* and measurements of Th1 (Interferon-gamma) and Th2 (Interleukin-4) cytokines will be performed using ELISA. The time points assayed will be day 1, day 43 and day 50.
- Biopsies taken on day 45 will be used to assess expression of inflammatory markers.
- Feeding on human volunteers: 24 hour after emergence from pupae, male and female *Aedes aegypti* and *Aedes albopictus* mosquitoes will be allowed to mate for 24-48 hours. After this period, female mosquitoes will be separated from males. These mosquitoes would have only been sugar-fed up until now. Female mosquitoes will be placed in a secured Plexiglass feeding device and allowed to feed on the volunteer's arms on Day 43 (approximately 21 days after they have completed the vaccination schedule). Each participant from each arm will be exposed to the bites of *Aedes aegypti* on the right arm and *Aedes albopictus* on the left arm. Mosquitoes that had a blood meal will then be removed and followed up to assess any changes to their life cycle, i.e., life-span, number of eggs laid, number of fertile eggs, number of surviving larvae etc. The mosquito colony used in this study will not be fed on human blood before exposure to participants, but on non-mammalian blood to minimize the presence of blood borne pathogens.
- Zika virus killing, *in vitro* toxicity assay:
  - Blood samples will be obtained from all volunteers 21 days after vaccination is completed (day 43 pre-feeding). PBMCs+sera containing immune cells and antibodies generated against AGS-v PLUS will be tested for their ability to kill or inactivate Zika virus coated with salivary gland proteins from *Aedes aegypti* and *Aedes albopictus*. Viability of the virus will be tested by infecting Vero cells with the PBMC/virus supernatants. Infectivity of the Zika virus will be assessed by measuring the viability of the Vero cells using MTT assay.
  - Zika virus will be obtained from commercial suppliers and will be propagated *in vitro*.

## 7.2 Reactogenicity

On a daily basis during the 7-day period after each injection participants will evaluate and record temperature, any local (redness, swelling, and pain) or general symptoms (e.g., fever, chills, headache, myalgia, arthralgia, malaise, sweats, fatigue, nausea, vomiting) they experience on the AE memory aid. At the day 8 and day 29 visits (phone call) the AE memory aids will be reviewed via phone and study staff will record reactogenicity during their discussion with each participant.

The AE memory aid will be completed by the participant in the evening. Participants will be instructed on how to complete the card.

## 7.3 Mosquito Bite Assessment

Mosquito bites will be assessed by the PI or trained study staff on days 43 (30 minutes after mosquito feeding), 45, and 50. Local reaction will be assessed by grading the size in mm of redness and swelling/induration.

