
Primary Endpoints:
	
 
1. Incidence and severity of treatment emergent adverse events (AEs) and serious adverse events (SAEs).
 
2. Geometric mean titer and fold increase in serum AGS-v PLUS specific immunoglobulin G (IgG), immunoglobulin M (IgM) and immunoglobulin E (IgE) titers from day 1 to day 43.
 
3. Geometric mean concentration and fold increase in Type 1 and Type 2 T-helper cell (Th1 and Th2) cytokine responses (from day 1 to day 43) after in vitro exposure of PBMCs with AGS-v PLUS antigens.
 

Secondary Endpoints:
	
 
1. Geometric mean titer and the fold increase in AGS-v PLUS specific IgG, IgM and IgE titers seven days after mosquito feeding (day 50) compared to day 1 and day 43 titers.
 
2. Geometric mean concentration and fold increase in AGS-v PLUS specific Th1 and Th2 cytokine responses in the supernatants of PBMCs (day 50 compared to days 1 and 43) after in vitro exposure with AGS-v PLUS.
 
3. Survival and fecundity in Aedes aegypti and Aedes albopictus female mosquitos after feeding on vaccinated participants.
 

Exploratory Endpoints:
	
 
1. Reactions to the mosquito bites by size of wheals/papules, redness of the flare, swelling and itching 30 min post-mosquito feeding (day 43), after 2 days (day 45) and after 7 days (day 50).
 
2. Early innate immune response to the mosquito bites in AGS-v PLUS vaccinated participants compared to placebo from biopsies taken from the bite site 2 days post-feeding.
 
3. In vitro viability of Zika virus coated in mosquito saliva after incubation with serum and/or PBMCs from vaccinated participants.
 
4. Geometric mean concentration and fold increase in Th1 and Th2 cytokine responses (from day 1 to day 43, and from day 43 to day 50) after in vitro exposure of PBMCs with mosquito saliva from Aedes aegypti, Aedes albopictus and Anopheles gambiae.
 

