Mosquito saliva contains a range of molecules including vasodilators, anticoagulants and immunomodulators whose purpose is to prevent the disruption of feeding by the host. Mosquito saliva has been shown to inhibit T and B cell proliferation and downregulate the expression of interferon gamma (IFN- $\gamma$ ), a soluble Type 1 T helper cell (Th1) pro-inflammatory immune mediator known to have *in vivo* therapeutic and prophylactic effects against other arthropod-transmitted diseases such as leishmaniasis. Interestingly, mosquito saliva also triggers a non-inflammatory Type 2 T helper cell (Th2) host immune response that causes the characteristic irritation and allergic reaction associated with mosquito bites. With time and continuous exposure, individuals become desensitized to mosquito bites due to a reduction in Th2 cytokine mediators, thus allowing for a more effective development of pro-inflammatory Th1 responses. Moreover, exposure to bites from uninfected mosquitoes reduces the development of *Plasmodium yoelii* in its murine host and that this protection is associated with a shift to a Th1 response at the bite site after repeated exposure to mosquito saliva.

Research has shown that mosquito-injected sporozoites can remain at the bite site for at least 5 minutes, enter general circulation by 15 minutes with most gone from the initial bite site by 60 minutes. During this time, it has been suggested that *Plasmodium* can evade the immune system and travel away from the bite site to the liver via the lymphatic system by infecting activated and non-activated macrophages. Activated macrophages can and do kill parasites that infect them (e.g., *Leishmania* and *Plasmodium*), but non-activated macrophages are unable to do so. Macrophage activation is characteristic of a Th1 response and is inhibited by the Th2 response triggered by mosquito saliva. This same process of downregulation of Th1 cytokines by modulation of the host immunity towards a Th2 response at the bite by the mosquito saliva has been reported to facilitate the transmission of chikungunya virus, and arboviruses in general.

[figure not shown]

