### Exploratory:

1. Reactions to mosquito bites by size of wheals/papules, redness of the flare, swelling and itching 30 min post-mosquito feeding (day 43), after two days (day 45) and after 7 days (day 50).
2. Early innate immune response to the mosquito bites in AGS-v PLUS vaccinated participants compared to placebo from biopsies taken from the bite site 2 days post-feeding.
3. *In vitro* viability of Zika virus coated in mosquito saliva after incubation with serum and/or PBMCs from vaccinated participants.
4. Geometric mean concentration and fold increase in Th1 and Th2 cytokine responses (from day 1 to day 43, and from day 43 to day 50) after *in vitro* exposure of PBMCs with mosquito saliva from *Aedes aegypti*, *Aedes albopictus* and *Anopheles gambiae*.

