### 14.3 Analysis Plan

T-tests will be used to compare immunogenicity endpoint measurements for the primary endpoint and other continuous endpoints between each treatment group and the placebo group. For binary endpoints Fishers exact test will be used. AEs will be tabulated by treatment arm.

The fold increase in cellular and humoral responses to AGS-v PLUS from day 1 to days 43 and 50, and from day 43 to day 50 will be calculated for each participant. The mean fold increases on each active group will be compared to the mean fold increases in the placebo group. The geometric mean antibody titers and geometric mean cytokine concentrations to AGS-v PLUS on days 1, 43, and 50 will be calculated and compared between the different treatment groups.

The fold increase in cellular responses to mosquito saliva from day 1 to days 43 and 50, and from day 43 to day 50 will be calculated for each participant. The mean fold increases on each active group will be compared to the mean fold increases in the placebo group. The geometric mean cytokine concentrations to mosquito saliva on days 1, 43 and 50 will be calculated for each treatment group and compared to placebo.

For the mosquito analysis, the following parameters will be compared on the active groups versus placebo for each mosquito (*Aedes aegypti* and *Aedes albopictus*):

- mean number of days mosquitoes survive after feeding on vaccinated participants
- mean number of eggs laid
- mean number of mosquitoes emerging from the laid eggs

For the visual assessment of the mosquito bite the following parameters will be calculated for each group and active groups will be compared to placebo at three different time points: day 43 (30 min post feeding), day 45 and day 50:

- mean number of visible bites
- mean redness measured across the widest part (mm)
- mean swelling measured using the ball point pen method (mm^2). Ball point pen measurement of induration uses the pen to slide on top of the skin so it halts at the edge of true induration (versus redness)

From the biopsies taken on day 45, the following comparisons will be made:

-gene expression: the level of expression of inflammatory cytokines at the bite site compared to normal skin (control) will be calculated for each participant for each mosquito bite. The mean will be calculated in each group and compared to placebo.

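### The exploratory bite-reaction endpoint names itching and wheal/papule size, but the bite assessment and the analysis plan list neither, and swelling changes from mm to mm² between them

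*Combined protocol and SAP*

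**What the plan says.** **Endpoint.** Section 3.2 defines exploratory endpoint 1 as "Reactions to mosquito bites by size of wheals/papules, redness of the flare, swelling and itching 30 min post-mosquito feeding (day 43"), and again at Days 45 and 50. The Protocol Summary gives the same four components.

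**Measurement.** Section 7.3 has the bites assessed on the same three days and specifies: "Local reaction will be assessed by grading the size in mm of redness and swelling/induration". The visit descriptions (Sections 6.6 to 6.8) and Appendix A schedule a bite assessment without listing further items.

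**Analysis.** Section 14.3 compares each active group with placebo at the three times on "mean number of visible bites", on "mean redness measured across the widest part (mm") and on "mean swelling measured using the ball point pen method", the last in mm².

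**Layout of the feeding.** Section 6.6 exposes the right arm to *Aedes aegypti* and the left arm to *Aedes albopictus*. On Day 45 (Section 6.7, with detail under Risk of Skin Biopsies in Section 8) one bite on each arm is biopsied, plus a control site of unbitten skin.

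**The concern.** The endpoint, the procedure that should supply its data and the analysis that should use them describe three different sets of variables. A site that follows Section 7.3 exactly will reach Day 50 without a solicited itch rating. A statistician who follows Section 14.3 exactly will report on neither itching nor wheal/papule size, and will need a swelling area whose derivation is not written down.

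Section 1 gives a reason to want the symptom as well as the size of the reaction. It says that saliva triggers a Th2 "host immune response that causes the characteristic irritation and allergic reaction associated with mosquito bites", and that the vaccine is intended to induce a Th1 response. Bite irritation is therefore something that the protocol's own rationale suggests could change.

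There is one feeding per participant, and Section 6.6 allows a single repeat only for absent or poor feeding. Itch data not collected between Days 43 and 50 are lost. The swelling formula matters for a second reason: unblinding follows once data up to Day 50 are collected, and a conversion chosen after that could be influenced by the results.

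**Working it through.** The plan states no figure for this endpoint, so the check is a line-by-line comparison.

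| Component | Endpoint (Summary, 3.2) | Bite assessment (7.3) | Analysis (14.3) |
|---|---|---|---|
| Flare redness | named | mm | mm, widest extent |
| Swelling | named | mm, as swelling/induration | mm², ball-point pen |
| Wheal/papule size | named, separately from swelling | not named | not named |
| Itching | named | absent | absent |
| Number of visible bites | not named | not named | compared |

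Of the four endpoint components, one (redness) agrees in all three places. One (swelling) appears in all three with conflicting units. Two appear in the endpoint alone.

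**Other possible sources of the missing items**

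- Section 6.1 has a 0 to 3 scale, but it is used once, at screening, for the usual overall response to bites. It does not rate itching after the study feeding.
- The memory aid (Section 7.2) covers the 7 days after each injection, not the feeding, and its listed symptoms do not include itching.
- Appendix C has no row for itching or local bite reactions.
- Adverse events are assessed on Days 43, 45 and 50 (Sections 6.6 to 6.8) and elicited by questioning (Section 12.1). Pruritus is a named feeding risk (Section 8.5), and every AE is graded (Section 12.3.1). This route can yield a graded itch event. It does not require a rating from every participant or for each arm, and Section 14.3 only tabulates AEs by treatment arm.

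**Number of ratings.** A solicited rating per arm would give 50 participants × 2 arms × 3 times = 300 planned values, assuming full attendance. The plan specifies none of them.

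**Swelling unit.** One reading in mm does not fix an area in mm². Take an assumed reading of d1 = 10 mm:

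- circle: π/4 × 10² = 78.5 mm²
- product of two equal diameters: 10 × 10 = 100 mm²
- ellipse with an assumed second diameter of 5 mm: π/4 × 10 × 5 = 39.3 mm²

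The same reading can thus give 39.3 to 100 mm², depending on a second diameter and a formula that the plan does not state. This shows the ambiguity only; it does not estimate an error in this trial.

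**The case against.** The strongest reply is that itching is not ignored. It is a foreseen risk, participants are asked about adverse events at all three visits, and each event receives a severity grade. Section 8.2 shows that in the earlier AGS-v trial bite erythema and swelling on feeding day were reported as graded AEs. This stands: a reader might infer that no itch severity could be recorded at all, and the documents do not support that. What is missing is a solicited rating for each arm and a planned comparison. Case report forms and a manual of procedures are mentioned but not available, and they might contain an itch item. Section 7.3 does not refer to them, and Section 14.3 would still not analyse it.

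Second, wheals and papules are raised lesions, and swelling/induration may be how they are sized. That is possible. The endpoint lists them separately, so the text is ambiguous; wheal/papule size is not shown to be unmeasured.

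Third, mm readings and a mm² variable are compatible if two diameters are taken, and nothing says that only one is. This also stands. The units are an unspecified conversion, not an impossibility. A reader might attach an error factor by treating the widest diameter as a circle, but the plan states no such rule and any factor would reflect the shape assumed.

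Fourth, a reader might infer that itching is the most direct clinical sign of the mechanism. Section 1 speaks of irritation and allergic reaction, not itching, and the trial measures the mechanism more directly through interferon-gamma, interleukin-4, IgE and bite-site gene expression.

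**Conclusion.** The inconsistency is real and of moderate importance. Itching is a named component with no bite-assessment item and no analysis in the plan. Wheal/papule size is undefined relative to swelling/induration. Swelling has two units and no stated conversion. As written, exploratory endpoint 1 cannot be reported in full as defined, although redness can, and swelling can once a conversion is fixed.

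The endpoint is exploratory and has no power statement of its own, and no primary or secondary conclusion depends on it. The conclusion rests on the protocol text alone and assumes that no document outside it adds the missing items.

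**What to change.** Before the first mosquito feeding, reconcile the Protocol Summary and Sections 3.2, 7.3 and 14.3.

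1. **Itching.** In Section 7.3 add a solicited rating for each arm at Days 43, 45 and 50, for example none, mild, moderate or severe (0 to 3). It should be defined for itching, not borrowed from the screening scale. Take it before the biopsy on Day 45 and exclude the biopsied bite on Day 50, so that wound healing is not scored as bite itch.
2. **Wheal/papule size.** State whether it is the swelling/induration reading or a separate diameter in mm.
3. **Swelling.** Record two perpendicular ball-point-pen diameters, d1 and d2, and state area = π/4 × d1 × d2. Use one unit in Sections 7.3 and 14.3.
4. **Several bites on an arm.** State how they are combined, for example the mean over visible, unbiopsied bites.
5. **Analysis.** In Section 14.3 add itching, and wheal/papule size if separate, active groups against placebo by species at the three times.

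If the sponsor does not want these components, remove them from the endpoint in the Summary and Section 3.2, and still settle the swelling unit and formula.

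The cost is one question per arm and extra ruler readings per bite at visits already held, a few minutes each, plus case report form lines and wording changes. Removing the components instead costs only wording, but gives up the itch data.

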## 8 Potential Risks and Benefits

### 8.1 Risks of Placebo administration

Subcutaneous injection of sterile saline poses minimal risk. The primary risks of placebo administration are a local injection-site reaction or infection at the site of injection. Signs of a local injection-site reaction include pain, swelling, and redness at the site of injection. These reactions resolve after short period of time and pose little risk to the participant. Applying cold packs and administering over the counter pain medications if necessary can generally treat these reactions. Signs of infection include pain, redness, swelling, edema, and purulent drainage at the site.

### 8.2 Risks of AGS-v PLUS ± adjuvant vaccination

Vaccine reactions must be considered a risk of all vaccines. These include minor and severe vaccine reactions. A minor vaccine reaction typically occurs within a few hours of injection and resolve within a short period of time posing little risk to the participant. Symptoms include local pain, swelling, and redness at the site of injection and may include systemic symptoms like fever, malaise, muscle pain, headache, and loss of appetite. Severe reactions usually do not result in long-term problems for the participant, but can be disabling. They are rarely life threatening, but can be in <0.5% of individuals. These reactions can include severe anaphylactic reactions and seizure. Topical symptomatic therapy may be administered if necessary to treat vaccine reactions including cold compresses, and topical anti-pruritic and pain relief. Additional standard of care therapy for pain or anaphylaxis will be administered according to CVD standards if the reaction becomes severe or life threatening.

The Sponsor has carried out a similar study testing the safety and immunogenicity of AGS-v, a vaccine that contains four of the five peptides in AGS-v PLUS (NCT 03055000). No safety concerns were raised by the safety review committee during the trial.

The manufacturer, SEEK, has completed clinical trials in the European Union for the FLU-v and HIV-v vaccines. The technology utilized for peptide identification, vaccine development and manufacturing for the FLU-v and HIV-v vaccines is the same technology utilized for AGS-v PLUS vaccine. FLU-v, HIV-v and AGS-v all utilize Montanide ISA-51 as the adjuvant too. Therefore, we expect similar safety findings for AGS-v PLUS as were observed with FLU-v, HIV-v and AGS-v. Below is a brief safety summary for all trials above mentioned:

- Phase 1 AGS-v 001: Safety issues had been mild in severity. The vaccinations were well tolerated. In the unadjuvanted AGS-v group the most common AEs were Grade 1 or 2 injection site pain, fatigue, and headache (37.5%, 31.3%, 31.3% of participants respectively). Some participants also experienced Grade 1 or 2 systemic reactions of myalgia/feverishness/chills/diaphoresis (6.1-18.8% of participants). The adjuvanted AGS-v group experienced a higher level of related AEs, with the most common being injection site pain, swelling, erythema, and pruritis (52.9%, 47.1%, 41.2%, and 41.2% respectively). They also experienced some systemic grade 1 and 2 AEs such as fatigue (41.2%) and feverishness (35.3%), as well as myalgia, chills and diaphoresis (5.9-29.4%). The placebo group experienced fewer AEs with only injection site pain and erythema in 25% and 6.3% respectively. They experienced a smaller amount of systemic AEs as well ranging from 6.3% to 12.5% for headache, fever, chills, fatigue, and myalgia. The most common AEs on Mosquito Feeding Day were Grade 1 erythema (93.8%) and Grade 1 local swelling (93.8%).
- Phase 1 FLU-v-001: no deaths occurred and only one SAE was reported with this being considered unrelated to FLU-v (appendicitis). There was no apparent increase in adverse events (AEs) with a change in dose from the 250 µg or 500 µg (500 µg of FLU-v is the equivalent of 825 µg of AGS-v as both contain 50 nmol of each peptide and a total of four peptides), but an approximate two-fold increase in AEs was seen in the adjuvant versus non-adjuvant groups. This latter point is likely responsible for the largely local administration site reaction AEs, and the forearm site and 1 ml volume is suspected to be the cause rather than the adjuvant itself. In conclusion, no safety or tolerability concerns were identified.
- Phase 1b FLU-v-002: all 32 participants reported AEs: 32 mild, 10 moderate and one severe (a pre-syncopal episode in the placebo group). There were no deaths or SAEs. The most frequently reported AEs were related to the injection site reactogenicity and are consistent with those already documented with use of the adjuvant. There were no other clinically significant changes in the other safety parameters (complete physical examination, clinical chemistry, hematology and urinalysis, vital signs including oral temperature, electrocardiogram [ECG]).
- Phase 2b FLU-v003: A total of 175 participants were enrolled to take part in a study carried in the Netherlands as part of a large European Consortium (UNISEC). Participants were allocated (2:2:1:1) to receive: 2 doses non-adjuvanted FLU-v, 1 dose of FLU-v adjuvanted in Montanide ISA-51, 2 doses of non-adjuvanted placebo or 1 dose adjuvanted placebo. The FLU-v vaccine formulations were safe and tolerated. A small number of participants mainly in the adjuvanted FLU-v group experienced severe reactions at the injection site that resolved with the use of over the counter anti-inflammatory drugs and required no additional follow-up by the medical team. The majority of solicited AEs that were related to the vaccination were observed at the site of injection and those were mild to moderate in intensity. An increase in the number of adverse

events was observed with the addition of adjuvant Montanide ISA-51 to the formulation. It is well known that emulsions prepared in this adjuvant have a tendency to create indurations at the site of injection which slowly disappear as the antigen is processed and the water in oil emulsion is degraded. Adjuvanted placebo had considerably more treatment emergent adverse events (TEAEs) definitely related to treatment than non-adjuvanted placebo (74.1% vs 18.8% participants). Addition of FLU-v to the placebo formulations increased the number of participants experiencing TEAEs (74.1 % to 93% of participants in adjuvanted placebo to adjuvanted FLU-v, and 18.8% to 34.5% participants in non-adjuvanted placebo to non-adjuvanted FLU-v). This indicates that the antigen itself is immunogenic and induces a small inflammatory reaction that translates into AEs at the injection site. These AEs were mostly mild to moderate with the participants in adjuvanted FLU-v group showing the highest number of these AEs. A total of 20 participants experienced adverse events classified as severe in intensity with only 7 of them being definitely related to the study drug and defined as reactions at the site of the injection (1/58 in non-adjuvanted FLU-v, 5/57 in adjuvanted FLU-v, 0/32 in non-adjuvanted placebo and 1/27 in adjuvanted placebo).

- Phase 2b FLU-v004: 121 participants were randomized (1:1:1) into one of three arms: 2 doses adjuvanted placebo (Montanide ISA-51+WFI), two doses adjuvanted FLU-v or one dose adjuvanted FLU-v +adjuvanted placebo. Participants were then challenged with an H1N1 influenza virus. Overall the data showed a good safety profile for the IMP. The single dose FLU-v showed a better profile than the 2 doses. However, there were no significant issues with the single dose arm and no concerns with the 2-dose arm. Injection site reactions were as expected and of an 'acceptable' level. A greater incidence of local reactions was seen in active arms, which may suggest a local reaction to the protein in addition to the adjuvant. The number of definitely related AEs in both FLU-v treatment groups was considerably higher than the placebo but of similar severity. The main AE was induration at the site of the injection and was considerably higher in the vaccine groups than placebo (46.8% and 60.8% compared to 18%).
- Phase 1b HIV-v-001: all 59 participants reported an AE. Fatigue and injection site pain were the most commonly reported AEs. The majority of AEs were of mild severity (69.7%). There were 5 SAEs in 3 participants with 3 SAEs occurring in the one participant and only 2 SAEs occurring within 30 days of vaccination. None of the SAEs were considered to be related to the study drug. No participants died and no participant discontinued the study due to an AE.

